 - Treatment arm (explanatory variable of interest)
 - Center as a random effect (multiple patients per center)
 - Patient as a random effect (multiple measurements per patient)
 - Visit (temporal chronological variable)
 - Interaction between the treatment arm and the presence of a relapse during follow-

up

- A second mixed-effects regression model will be used to compare the M24 scores of the outcome measures while adjusting for baseline scores (M0):
 - M24 score (outcome variables)
 - Treatment arm (explanatory variable of interest)
 - Center as a random effect (multiple patients per center)
 - M0 score (adjustment variable)

- Interaction between the treatment arm and the presence of a relapse during follow-up

Secondary Objective F: Evaluate treatment tolerance on:

a. The occurrence of AEs and SAEs

- b. Pharmacological measurement of serum concentrations of 25(OH)D2 and 25(OH)D3
- c. Measurement of serum calcium, urinary calcium, and renal function

The number of AEs and SAEs per patient will be described by arm.

For points b and c, a mixed-effects regression model will be used to compare the evolution of measurements during follow-up. The model variables will include:

- Measurements at different visits (outcome variable)
- Treatment arm (explanatory variable of interest)
- Center as a random effect (multiple patients per center)
- Patient as a random effect (multiple measurements per patient)
- Visit (temporal chronological variable)

Secondary Objective G: Initial formulation: Correlate the variation in clinical and imaging parameters with the initial level and changes in the levels of 25(OH)D2 and 25(OH)D3 under treatment.

Reformulated Objective G1: Study the link between the severity of impairment (parameters measured by the baseline MRI, such as the number of lesions, EDSS score) and the vitamin D level measured during pre-screening (25(OH)D2 and 25(OH)D3).

A mixed-effects regression model will be estimated. The model variables will include: - Severity of impairment at inclusion (outcome variable). Several variables will be successively modeled: binary variables for MRI parameters (using a logistic regression model) and a quantitative variable for the EDSS score.

- Levels of 25(OH)D2 and 25(OH)D3 at pre-inclusion (explanatory variables of interest)
- Treatment arm (adjustment variable)
- Center as a random effect (multiple patients per center)

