baseline MRI scan for that patient if known. If the latter is also missing, the gadoliniumenhancement status used as the randomization stratification variable will be employed.

- When the date of the CIS is missing, it will be extrapolated from the date of the diagnostic MRI scan plus the median time between the CIS and the diagnostic MRI scan.

If the number of T2/FLAIR lesions (used as an indicator of lesion burden, in two categories "<9 lesions " and " >= 9 lesions ") at the baseline MRI is missing, it will be analyzed in a third category "Number of Lesions Missing".

- If the EDSS score is missing at baseline, it will be imputed by the first non-missing EDSS scores at the M3 and M12 visits, subtracting the median of the EDSS score difference between M0 and M3 (respectively between M0 and M12) obtained from patients with scores recorded at both visits. If the result is negative, the median will not be subtracted.

For other secondary outcome measures, no method for imputing missing data is planned.

Analysis population:

Patients who did not receive the study treatment will not be considered in the analyses, which will be conducted on a modified intention-to-treat basis.

All patients who received at least one dose of the study treatment will be included in the analyses.

Thus, the following individuals will not be considered in the analyses:

- Patients with "Study discontinuation at the investigator's decision due to disease activity identified on the baseline MRI" or occurrence of a relapse before treatment onset.

- Patients who withdrew their consent.

- Patients who did not undergo a baseline MRI (withdrawal of consent, inability to undergo MRI).

- Patients lost to follow-up immediately after inclusion (at the inclusion visit and/or baseline MRI), with no follow-up data.

- Patients mistakenly included without MS or with occurrence of a relapse before the baseline MRI.

These patients cannot be included in an intention-to-treat analysis because they have no follow-up and, therefore, no information on disease activity during follow-up.

Bibliographic References

Edgar et al 2021 : Including random centre effects in design, analysis and presentation of multi-centre trials. Trials. 2021, 22:357.

Kahan 2014 : Accounting for centre-effects in multicentre trials with a binary outcome – when, why, and how? BMC Medical Research Methodology, 2014, 14:20.

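### Objective G1 uses only baseline data, yet the single dosed-only analysis set removes patients for early disease activity, on a lack-of-follow-up reason that does not apply to G1

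*SAP*

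**What the plan says.** Under Secondary Analyses, Reformulated Objective G1 looks for an association between two baseline quantities. One side is "severity of impairment (parameters measured by the baseline MRI, such as the number of lesions, EDSS score"). On the other side stands pre-treatment vitamin D, taken at pre-screening as 25(OH)D2 plus 25(OH)D3. The dependent variable is "Severity of impairment at inclusion (outcome variable"). Several outcomes are modelled in turn: "binary variables for MRI parameters (using a logistic regression model) and a quantitative variable for the EDSS score". The explanatory variables are the pre-inclusion 25(OH)D2 and 25(OH)D3 levels, with treatment arm as an adjustment variable and center as a random effect.

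The Analysis population section then sets one population: "Patients who did not receive the study treatment will not be considered in the analyses, which will be conducted on a modified intention-to-treat basis". It lists the groups left out, beginning with "Patients with 'Study discontinuation at the investigator's decision due to disease activity identified on the baseline MRI' or occurrence of a relapse before treatment onset". The list also names consent withdrawals, patients without a baseline MRI, patients lost straight after inclusion, and patients included by mistake without MS or with a relapse before the baseline MRI. One reason covers the whole list: "These patients cannot be included in an intention-to-treat analysis because they have no follow-up and, therefore, no information on disease activity during follow-up". No exception is made for G1, there or elsewhere.

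**The concern.** G1 is a cross-sectional analysis. Outcome and exposure are both measured before treatment, so a patient who was never dosed and never followed can still contribute. A patient stopped because of what the baseline MRI showed has had that MRI, and it is the scan from which G1 takes its MRI outcomes.

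The rule thus removes patients towards the active end of the disease spectrum that G1 tries to explain. If low vitamin D goes with more active disease, some of the patients who would show it are taken out, and G1 tends to understate the link. This bears only on the validity of a secondary association. No randomised comparison depends on it.

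**Working it through.** **1. The reason for exclusion against what G1 needs.**

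| Item | SAP source | Needs dosing or follow-up? |
|---|---|---|
| G1 outcomes: baseline MRI parameters, EDSS | Reformulated Objective G1 | No |
| G1 exposure: 25(OH)D2 and 25(OH)D3 at pre-screening | Reformulated Objective G1 | No |
| Reason for exclusion: no follow-up | Analysis population | Concerns follow-up outcomes only |

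The stated reason fits EDA, relapse counts and M24 scores. It does not fit G1.

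**2. How the exclusion relates to each G1 outcome.**
- Baseline MRI activity as a binary outcome: selection is on the outcome itself.
- Number of lesions and EDSS: selection is on something correlated with the outcome.
- Relapse before treatment: selection is indirect, through its link with severity.

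**3. Size for EDSS.** The SAP gives no figure for G1 and no number removed, so there is nothing to reproduce and every input below is an assumption. Take EDSS and vitamin D as standardised normal variables with correlation −r, r = 0.2. Let the activity behind removal have correlation ρ with EDSS and be related to vitamin D only through EDSS. Remove the top fraction p on activity. With c the normal quantile at 1 − p, h = φ(c)/(1 − p) and k = h(h + c), the slope after selection divided by the full slope is

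(1 − kρ²) / (1 − kρ²r²).

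The values of k are:
- p = 2%: c = 2.054, h = 0.0494, k = 0.104
- p = 5%: c = 1.645, h = 0.1086, k = 0.190
- p = 10%: c = 1.282, h = 0.1950, k = 0.288

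Worked case, p = 10% and ρ = 0.5: kρ² = 0.0720, so the ratio is 0.9280/(1 − 0.0720 × 0.04) = 0.931, a loss of 6.9%.

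| Loss of EDSS slope | p = 2% | p = 5% | p = 10% |
|---|---|---|---|
| ρ = 0.3 | 0.9% | 1.6% | 2.5% |
| ρ = 0.5 | 2.5% | 4.6% | 6.9% |
| ρ = 0.8 | 6.4% | 11.8% | 17.8% |
| ρ = 1.0 | 10.0% | 18.4% | 28.0% |

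Simulation with 2,000,000 subjects agrees for ρ = 0.3 and 0.5 to within 0.1 percentage point.

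**4. A second model, with removal by decision.** Here a fraction of patients with binary MRI activity is dropped at random, rather than the whole top tail. The simulation has 400,000 subjects, a vitamin D coefficient of −0.3, about 30% active, and a shared latent severity. All of these are assumed.

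| Share of all patients dropped | EDSS slope | OR, ≥9 lesions | OR, activity |
|---|---|---|---|
| 0% | −0.150 | 0.776 | 0.780 |
| 9% | −0.147 | 0.779 | 0.779 |
| 15% | −0.144 | 0.783 | 0.782 |
| 24% | −0.137 | 0.791 | 0.782 |

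The slope loses 2%, 4% and 9% (for example 1 − 0.137/0.150 = 8.7%). The odds ratio for ≥9 lesions moves slightly towards 1. The odds ratio for activity itself barely moves, but the prevalence of activity falls from 30% to 8%, so precision is lost. If all active patients were removed, that outcome could not be modelled.

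**The case against.** The strongest reply is that the bias is probably small and that literal selection on the outcome does little harm here. The MRI parameters are modelled by logistic regression, and selection purely on a model's own binary outcome leaves the odds ratio almost unchanged. For lesion number and EDSS, the bias depends on a correlation that the SAP does not give. This stands, and it sets the size of the point.

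A reader might infer from the ρ = 0.8 and 1.0 rows that G1 loses up to 28% of its slope. The document does not support that. Those rows mean removing patients almost on EDSS itself, and removing the whole top tail. The SAP's rule needs an investigator's decision to stop, or a relapse. The Primary Analysis section also keeps contrast enhancement on the reference MRI as a candidate adjustment variable, which suggests that patients with enhancement remain in the set.

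Three further points stand in part.
- The count of 316 patients (lesion-load paragraph) is not said to be before or after exclusions, so a percentage removed cannot be turned into a firm number.
- Some excluded patients could not or should not enter G1: those without a baseline MRI have no MRI outcome, and those included by mistake without MS do not belong in an MS severity analysis.
- The SAP does not show that baseline measures of undosed patients were recorded in the modelled form; FLAIR volume was available for only 258 of the 316.

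For scale, with n = 316 and r = 0.2 the standard error of the standardised slope is √(0.96/314) = 0.055. A 7% loss is 0.014, about a quarter of one standard error.

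None of this supplies a reason for applying a follow-up criterion to a baseline analysis.

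**Conclusion.** The point holds as a mismatch between the analysis set and the objective. As written, the SAP removes patients from G1 for disease activity related to its outcomes, and its only justification concerns data that G1 does not use.

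The expected consequence is modest attenuation: about 1% to 7% of the EDSS slope if 2% to 10% of patients are removed and activity correlates 0.3 to 0.5 with EDSS, and less if only part of the active tail is removed. Odds ratios for binary MRI outcomes correlated with activity move slightly towards 1. Where activity itself is the outcome, the cost is precision. Larger losses need stronger assumptions than the document supports, and the true number removed is unknown.

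A reader might also infer that the exclusions damage the primary analysis. This point gives no ground for that; it concerns G1 alone.

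**What to change.** Add one sentence to the Analysis population section. G1 is analysed in all included patients with a pre-screening 25(OH)D value and a recorded value of the baseline measure being modelled, whether or not they were dosed. Patients mistakenly included without MS, and those whose consent withdrawal covers use of their data, are left out. Report the modified intention-to-treat result for G1 as a sensitivity analysis, with the number of patients in each set. Keep the modified intention-to-treat set wherever follow-up is needed.

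The cost is small: a sentence of text, a slightly different denominator for G1, and use of baseline data only where already recorded. The SAP says that it was drafted before data lock and before analysis; a change at that stage needs no sight of results. Treatment arm may stay in the G1 model or be dropped. It cannot explain severity measured before treatment, but as a randomised covariate it does no evident harm.
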